8.7 Study Drug / Medical Device Accountability

The in-house Pharmacy will be responsible for maintaining accurate drug storage and dispensing logs including records about shipments to the trial sites, return to the Sponsor and document on-site destruction if applicable. Drugs will be stored in accordance with GCP and GMP requirements and will be inaccessible to unauthorized personnel. Lot/batch numbers will be recorded. All unused and used rhC1INH vials will be retained at the site until drug inventory has been completed by the Monitor.

The study staff will use study drugs only within the framework of this clinical study and in accordance with this protocol. Receipt, distribution, return, and destruction (if any) of study drugs will be properly documented. Accountability records will include dates, quantities, batch/serial numbers, expiration dates, and patient numbers and sign off by the pharmacist or nurse. These records will adequately document that the patients were provided the doses as specified in the protocol and should allow reconciliation activities from Monitor for all rhC1INH received from the Sponsor. The drug accountability process will be described in further detail separately in the Monitoring Manual.

8.8 Return or Destruction of Study Drug / Medical Device

Any study product that remains unused at the termination of the study will be returned to the manufacturer or destroyed in accordance with institutional policies and this process will be recorded.

9. STUDY ASSESSMENTS

9.1 Study Flow Chart(s) / Table of Study Procedures and Assessments

Study Periods	Screening	Intervention Period					Follow-up	
		1	2	3	4	5	6	7
Visit	1						6	7
Time (weeks or days, or hours)	d-1 ¹	d0	d1	d2	D3-13 during ad- mission	d14 (+/- 2d) or dis- charge	3 months post treat- ment) ⁹	
In- /Exclusion Criteria	x							
Patient Information and Informed Consent	x							
Randomization		x						
Demographics	x							
Medical History	x							
Physical Examination	x	x	x	x	x	x		
Vital Signs including Respiratory Rate ⁷		x	x	x	x	x		
Laboratory Tests (blood) ³		x	x	x	x	x		
Virology testing		x ²			x ²	x ²		
Administer Study Medication ⁴		x	x	x	x			
Assessment of WHO ordinal scale		x	x	x	x	x	x	x
Assessment of ICU admission and/or mechanical ventilation		x	x	x	x	x	x	x
Measure Oxygenation levels ⁸		x	x	x	x	x		
Monitoring QT intervals ¹⁰		x	x	x	x	x		
Prior/Concomitant Medications	x	x	x	x	x	x	x	x
Laboratory assessment in detail:								
Routine full blood count ³		x	x	x	x	x		
Routine coagulation studies ³		x	x	x	x	x		
Routine biochemistry including LDH ³		x	x	x	x	x		
Serum pregnancy test	x ⁵							
Ferritin, IL-6, D-Dimer ³		x	x	x	x	x		
C1INH concentration ⁶		x	x	x	x	x		
C1INH activity ⁶		x	x	x	x	x		
Complement proteins (e.g. C3, C4) ³		x	x	x	x	x		
(Serious) Adverse Events	x	x	x	x	x	x	x	x

¹Eligibility criteria to be assessed within 48 hours upon hospital admission.

²Inclusion of patients based on suggestive clinical symptoms and results from radiological studies will be possible. However, a nasopharyngeal swab for PCR validation of confirmed SARS-CoV-2 infection must be performed in all subjects no later after inclusion of the patients if not already performed before inclusion into the study. Subsequent virological testing for SARS-CoV-2 will be performed on day 4-7 (according to local standard) and again on day 14 if participants are still admitted.

³Routine laboratory tests will be performed once before 1st administration of study medication on (day 0 through day 3) and once daily during hospital admission according to standard procedures of the study site, but will include a set of hematology, coagulation and biochemistry parameters. Additional blood samples will be collected at the same time.

⁴IMP will be administered every 12 hours (+/-15 minutes) for 4 days. A total of 8 doses will be administered. Trial medication will be stopped in participants in whom PCR results are not consistent with confirmed COVID-19 and in patients that are discharged or transferred to another facility.

⁵A Serum hCG pregnancy test will be performed in women who may become pregnant, are sexually active, and do not use adequate contraceptive measures.

⁶Collection of samples will be once daily before 1st administration of study medication (day 0 through day 3) and once daily until hospital discharge.

⁷The worst value recorded on a given day will be documented.

⁸Oxygenation levels will be measured for patients on oxygen while hospitalized.

⁹3-months follow-up period begins post-treatment (Day 0). Assessments will be done daily until discharge and weekly via telemedicine interview or telephone call post-discharge.

¹⁰Monitoring of prolonged QT intervals in severely-ill subjects receiving multiple drugs.

Assessments of outcomes

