7.1 Eligibility Criteria

Participants fulfilling all of the following inclusion criteria are eligible for the study:

- Informed Consent as documented by signature,
- Male or Female age 18-85 years,
- Admitted to the hospital because of confirmed COVID-19 infection (by a positive SARS-CoV-2 PCR result),
- Expected to remain an inpatient over the next four (4) calendar days from time of enrollment,
- Evidence of pulmonary involvement on CT scan or chest X-Ray of the chest (e.g. ground glass opacities),
- Symptom onset within the previous 10 days OR shortness of breath within the previous 5 days. Symptoms include fever or one respiratory symptom (patients presenting later may have already progressed to an inflammatory state that is potentially not amenable to C1INH treatment). Respiratory symptoms include cough, sore throat, hemoptysis, shortness of breath, runny nose, or chest pain and
- at least one additional risk factor for progression to mechanical ventilation: 1) arterial hypertension, 2) >50 years, 3) obesity (BMI>30.0 kg/m²), 4) history of cardiovascular disease, 5) chronic pulmonary disease, 6) chronic renal disease, 7) C-reactive protein of >35mg/L, 8) oxygen saturation at rest in ambient air of <94%. Cardiovascular disease includes a history of coronary artery disease, cerebrovascular disease, peripheral artery disease, rheumatic heart disease, congenital heart disease and of

recent (< 3 months) deep vein thrombosis or pulmonary embolism. Chronic pulmonary disease includes a history of chronic obstructive pulmonary disease, asthma, occupational lung disease, interstitial lung disease or of pulmonary hypertension. Chronic renal disease is defined as a history of an estimated glomerular filtration rate (according to the Chronic Kidney Disease Epidemiology Collaboration equation) < 60ml/min/1.73 m² for at least three months.

*Also refer to the WHO definition for additional Cardiovascular diseases

The presence of any one of the following exclusion criteria will lead to exclusion of the participant:

- Contraindications to the class of drugs under study (C1 esterase inhibitor), e.g. known hypersensitivity or allergy to class of drugs or the investigational product,
- Treatment with tocilizumab or another IL-6R or IL-6 inhibitor (within 24 hours) prior to enrollment,
- History or suspicion of allergy to rabbits,

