8.6 Trial Specific Preventive Measures

All participants will receive standard supportive care established at the sites which may include off-label use of certain drugs that are deemed to be effective in COVID-19 (e.g. hydroxychloroquine, lopinavir/ritonavir). In addition, escalation of treatment with off-label use of certain drugs (e.g. tocilizumab) in deteriorating participants is allowed during the trial.

In terms of risk, rhC1INH, a recombinant human protein, has a very favorable side effect profile and major adverse events attributable to study medication are not expected in this study. Anaphylactic reactions are exceptionally rare and have only been observed in a single patient with a pre-existent allergy to rabbits. Although patients with rabbit allergy will be excluded from participating in the study, included subjects will be monitored for anaphylactic events during and for at least 12 hours after the last administration of rhC1INH. If patients develop type 1 allergic reactions following the administration of rhC1INH treatment according to in-house guidelines (potentially involving administration of antihistamines, corticosteroids, intravenous fluids and if needed adrenaline) will be provided.

No influence of rhC1INH on laboratory parameters or vital signs, including ECG was observed in previous clinical studies. Hence, we will not perform additional laboratory monitoring exceeding routine laboratory controls planned by the treating team (with the exception of the above-mentioned additional biomarker analyses). No interactions with other drugs are known.

If female, patients must be/have:

- Post-menopausal, defined as the absence of menses for at least one year, OR
Surgically sterile, defined as a bilateral tubal ligation at least 6 months prior to administration of study drug, bilateral oophorectomy, or complete hysterectomy, OR

- Using an effective means of contraception with a failure rate less than 1% per year (e.g. oral contraceptives, contraceptive injections, intrauterine device, double-barrier method, male partner sterilization), OR

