- A negative pregnancy test before study entry/randomization. We expect the rate of female patients of childbearing age who may become pregnant to be <10% of all patients potentially eligible for this study. Due to the short treatment period (4 days) and half-life of rhC1INH (2.5 hours) an effective means of contraception is not mandatory during the hospitalization treatment phase. At least one method of contraception (oral contraceptives, barrier methods, approved contraceptive implant or abstinence) is required for the entire follow up study period
- Concomitant Interventions (treatments)

All participants will receive standard supportive care established at the sites which may include off-label use of certain drugs that are deemed to be effective in COVID-19 (e.g. hydroxychloroquine, lopinavir/ritonavir, prophylactic anticoagulation). In addition, escalation of treatment with off-label use of certain drugs (e.g. tocilizumab) in deteriorating participants is allowed during the trial. Randomization will be stratified by site to compensate for different standards of supportive care. Off-label use of drugs for the treatment of COVID-19 will be recorded in the CRF. Escalation of treatment is one outcome of interest.

Patients are allowed to use all their regular medication during the trial. In addition, patients will receive all drugs required for the treatment of COVID-19 or its consequences. The care of the participant will remain unaffected by inclusion into the study or by study group assignment.

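### Eligible women on highly effective contraception, such as oral contraceptives, have no required pregnancy test, and protocol 7.1 and 8.6 conflict on entry without contraception and on accepted methods (minor)

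*Protocol*

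**What the plan says.** Four parts of the protocol bear on who is tested and which contraception counts.

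- **9.1, footnote 5** (attached to the screening serum test in the flow chart): "Serum hCG pregnancy test will be performed in women who may become pregnant, are sexually active, and do not use adequate contraceptive measures". SAP 5.3 and SAP 5.8 footnote 5 repeat this. Neither document defines *adequate*.
- **7.1** (same criteria in the synopsis): a woman of childbearing potential is excluded unless she uses oral contraceptives, a barrier method, an approved implant or abstinence. A separate criterion excludes women who are pregnant, are breast feeding or have a positive serum hCG at screening. Each criterion is sufficient alone: "The presence of any one of the following exclusion criteria will lead to exclusion of the participant".
- **8.6** opens with "If female, patients must be/have" and gives four alternatives joined by OR: post-menopausal; surgically sterile; "Using an effective means of contraception with a failure rate less than 1% per year", with the examples "oral contraceptives, contraceptive injections, intrauterine device, double-barrier method, male partner sterilization"; or "A negative pregnancy test before study entry/randomization". Its last part says contraception is not mandatory during in-hospital treatment, then adds: "At least one method of contraception (oral contraceptives, barrier methods, approved contraceptive implant or abstinence) is required for the entire follow up study period".
- **9.2.1, Visit 1** lists the pregnancy test only as applicable or if necessary.

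**The concern.** Footnote 5 directs the test at sexually active women without adequate contraception. Section 7.1 removes those who use no listed method whatever the test shows. The women of childbearing potential who can enrol are the ones using a method, and for those on a highly effective method no visible section orders a test. For them the positive-hCG exclusion depends on a result that nobody is told to obtain.

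An early unrecognised pregnancy could then be exposed to rhC1INH. The pregnancy provisions in 10.1.2 (withdrawal, reporting within 24 hours, follow-up of mother and child) act only once a pregnancy is known.

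The second issue is eligibility. A site working from 8.6 and a site working from 7.1 could decide differently on the same woman. Section 12.4 classes inclusion/exclusion deviations as major, so a site that relied on 8.6 could record a major deviation.

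**Working it through.** The plan gives no figure to reproduce. The main check sets the rules side by side for each type of woman of childbearing potential.

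| Contraception at screening | 7.1 | 8.6 | Footnote 5 |
|---|---|---|---|
| Oral contraceptives | Eligible | Met, no test needed | No test |
| Single barrier | Eligible | Not among the under-1% examples, so a negative test is needed | Depends on the meaning of *adequate* |
| Abstinence | Eligible | Unclear; not among the examples | No test, as not sexually active |
| Intrauterine device, injections or sterilized partner | Method not in the list | Met, no test needed | Depends on the meaning of *adequate* |
| None, sexually active | Excluded | Met at entry by a negative test | Tested |

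Three results follow.

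1. **Oral contraceptives are the clear gap.** They are named in both 7.1 and the 8.6 under-1% examples, so they count as adequate under either standard. Such a woman is eligible, and none of 8.6, footnote 5 and Visit 1 requires her to be tested.
2. **7.1 and 8.6 disagree on a woman using nothing at entry.** Section 8.6 lets her in on a negative test; 7.1 excludes her because she uses no method before randomisation. The follow-up sentence in 8.6 would require her to use a method later, so the conflict concerns entry.
3. **The method lists differ.** Injections, intrauterine device and male partner sterilization appear in the 8.6 examples. They do not appear in the list in 7.1, the synopsis or the last part of 8.6.

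**Size.** Inputs:

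- planned enrolment of 120 patients, 80 of them on rhC1INH (11.2);
- the expected share of "female patients of childbearing age who may become pregnant to be <10% of all patients potentially eligible" (8.6);
- a failure rate of 1% per year, the ceiling in 8.6;
- an assumed 4 to 8 weeks during which a pregnancy could go unrecognised (not in the documents).

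Women concerned, if enrolled patients mirror the eligible pool:

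- overall: fewer than 0.10 × 120 = 12
- on rhC1INH: fewer than 12 × 80/120 = 8

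Expected unrecognised pregnancies = women × annual rate × weeks/52:

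- 8 treated women, 4 weeks: 8 × 0.01 × 4/52 = 0.006
- 8 treated women, 6 weeks: 8 × 0.01 × 6/52 = 0.009
- 8 treated women, 8 weeks: 8 × 0.01 × 8/52 = 0.012
- all 12 women, 6 weeks: 12 × 0.01 × 6/52 = 0.014

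The counts 12 and 8 are ceilings, and the 7.1 contraception exclusion may lower them. The share of eligible women left untested cannot be computed, because no contraceptive mix is given. The expected number would be higher if users of less effective methods also went untested.

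**The case against.** The strongest reply is that this is a deliberate risk-based rule. For a woman on an under-1% method, 8.6, footnote 5 and Visit 1 all point the same way: test where contraception is weak. Few such women are expected, dosing lasts 4 days, the half-life is 2.5 hours, and 3.3 reports no embryofetal concern. Known pregnancy is excluded without a test, and nothing forbids testing. All of this stands, and it is why the point is minor. It does not settle the matter. Section 8.6 gives the short treatment and half-life as reasons for not mandating contraception in hospital, not for omitting a test. The risk-based reading also leaves the 7.1 and 8.6 conflict in place.

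A second reply is that excluding a positive hCG at screening implies that a test is done. An investigator could read it so. But it is a criterion about a result, and every statement of who is tested is conditional. A site could follow the schedule, skip the test and still comply. Consent pages were not available, so the finding covers only the visible text.

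Three stronger readings are tempting and not supported:

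- **That eligible women in general go untested.** Section 8.6 does require a negative test from a woman whose method falls short of the under-1% standard, such as a single barrier.
- **That users of an intrauterine device, injections or a sterilized partner would be turned away.** The 7.1 list omits these methods, but it does not say that only the listed ones count, and 8.6 names them as effective. This looks like a drafting slip.
- **That appreciable fetal exposure is likely.** The expected number is about 0.01.

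**Conclusion.** The point holds as a minor safety and eligibility-wording fix. An eligible woman on a highly effective method, most clearly oral contraceptives, has no required test behind the positive-hCG exclusion. Sections 7.1 and 8.6 give different answers for a woman using no contraception at entry, and their method lists do not match.

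The benefit in events is very small: about 0.006 to 0.012 unrecognised pregnancies among at most 8 treated women. That range rests on the two ceilings in 8.6, on enrolment mirroring the eligible pool, and on the assumed 4- to 8-week window. The case for change rests on an unenforced exclusion and contradictory entry rules, not on this count.

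The testing gap affects no efficacy analysis. The eligibility conflict could at most lead to a patient being classed as a major eligibility violation and left out of the per-protocol set; the primary FAS/ITT analysis is untouched.

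**What to change.** 1. In 9.1 footnote 5, 9.2.1 Visit 1, SAP 5.3 and SAP 5.8 footnote 5, require a negative serum hCG before randomisation in every woman of childbearing potential, regardless of contraception or sexual activity.
2. Replace the 8.6 list with: post-menopausal, OR surgically sterile, OR (a method accepted in 7.1 AND a negative serum hCG). Delete the separate under-1% alternative and its examples. If kept, they would have no function and would still disagree with 7.1.
3. Use a single method list in 7.1, the synopsis and the last part of 8.6, adding intrauterine device, injections and male partner sterilization.

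The statement that contraception is not mandatory during in-hospital treatment can stay.

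The cost is wording in the synopsis, four protocol sections and two places in the SAP; up to about a dozen extra serum hCG assays in enrolled women and a few in women who then fail screening; and a short wait for the result within the 48-hour screening phase. The assay is already scheduled at screening.

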9.1.1 Assessment of primary outcome

For the analysis of the primary endpoint, illness severity will be assessed on each day after enrollment (worst status) with the use of the WHO Ordinal Scale for Clinical Improvement and the score on day 7 will be analyzed stratified by its baseline value.

Patient State	Description	Score
Outpatient	No limitation in activities	1
	Limitation in activities	2
Hospitalized Mild disease	No oxygen therapy	3
	Oxygen by mask or nasal prongs	4
Hospitalized Severe disease	Non-invasive ventilation or high-flow oxygen	5
	Intubation, mechanical ventilation +/- additional organ support	6
Death	Death	7

Figure 3: WHO ordinal scale for clinical improvement.

The worst score on a given day (between 0:00 and 24:00 hours) will be used for the categorization

Patient State	Description	Score
Outpatient	No limitation in activities	1
	Limitation in activities	2
Hospitalized Mild disease	No oxygen therapy	3
	Oxygen by mask or nasal prongs	4
Hospitalized Severe disease	Non-invasive ventilation or high-flow oxygen	5
	Intubation, mechanical ventilation +/- additional organ support	6
Death	Death	7

9.1.2 Assessment of Secondary Outcomes

- For the analysis of time to clinical improvement of at least 2 points in the WHO Ordinal Scale for Clinical Improvement, clinical severity will be assessed every day until day 14 according to the Scale with the worst status for that day recorded.
- For the analysis of the proportion of patients alive and not having required invasive or non-invasive ventilation at 14 days after enrollment, admission to ICU with invasive or non-invasive ventilation or death will be assessed every day until day 14.
- For the analysis of the proportion of patients with ALI within 14 days after enrollment, PaO₂/FiO₂ will be determined daily until day 14. This is only relevant for patients with arterial blood gas sampling performed in the ICU or rarely in the medical unit.

9.1.3 Assessment of Other Outcomes of Interest

- The following assessments will be performed during the study: changes in WHO ordinal scale, ICU admission/discharge date, mechanical ventilation start/end date, admission/discharge date, all-cause mortality within 4 weeks.
- Supportive interventions provided to study subjects in addition to ventilatory support (e.g., the use of prone ventilation, high-frequency oscillatory ventilation (HFOV), paralytics, pulmonary vasodilators).
- The receipt of additional anti-inflammatory treatments such as tocilizumab will be recorded within 14 days.
- Vital signs will be recorded until discharge to determine the time to defervescence and clinical improvement.
- For the analysis of virological clearance of SARS-CoV-2, samples from the upper or lower respiratory tract will be collected at baseline (if not already performed on admission) to confirm SARS-CoV-2 infection and again on day 4-7 and day 14/discharge. Subsequently, samples will be analysed at the central laboratory of the study site using a quantitative assay according to validated standard in-house procedures. A negative result will be confirmed by a second test at least 12 hours apart.
- For the analysis in changes of biomarker levels CRP- LDH, D-dimer, IL-6 and lymphocytes will be measured in blood samples collected on day 0, 1-3 every day afterwards until day 14 or discharge. Blood samples will be sent to and analysed by validated methods in the central laboratory of respective study sites according to

standard in-house procedures.

- For the analysis of inflammatory proteins and cytokines blood samples will be collected on day 0, and daily until day 14 or discharge. For the analysis of rhC1INH pharmacokinetics (C1INH activity and concentration), blood samples will be collected at baseline, 5-10 minutes after the first administration and again immediately before and 5-10 minutes after a subsequent administration on day 1.

9.1.4 Assessment of Safety Outcomes

9.1.4.1 Adverse events

Participants will be followed for adverse events and outcomes for 3 months post treatment (Day 0). Assessments will be done daily while in the hospital and via a weekly follow-up telemedicine interview or telephone call after discharge.

Adverse events and clinical course including death within 4 weeks will be assessed by a weekly telemedicine or structured telephone interview for 3 months post-treatment. If necessary, medical charts will be reviewed, discharge summaries will be reviewed, or the patients' general practitioner will be contacted regarding specific follow-up information.

Every effort will be made to contact the trial subject and obtain complete data for follow-up. Conditions that started before signing informed consent will be recorded as medical history. Conditions that started or deteriorated after signing informed consent will be documented as AE. Definition of AE and SAE will be found in Section 10.

All AEs will be assessed and documented by the Investigators according to seriousness, intensity, causal relationship with study treatment, action taken with study treatment (e.g. withdrawal), specific treatment for AE and outcome. In addition, time of onset and AE duration will be recorded. Procedures are defined in Section 10. AEs will be recorded on the respective CRF pages. Participants will be asked about any new events/complaints during the hospitalization and up to 3 months post treatment. In addition, participants are asked to report any new events including hospital admission to the study team.

